## 14.1 Study Stopping Criteria

The following criteria will be used to determine whether and when to stop the study prior to meeting recruitment targets:

- If there are 3 cases where mail-order delivery of the medication is delayed by more than 7 days, we will temporarily halt the study and assess the need to adjust the inclusion criteria to less than 57 days' gestation (instead of 63 days) in order to eliminate the possibility that participants receive mifepristone past 70 days' gestation. We will also investigate all cases of medication delivery being delivered more than 4 days after the prescription was sent to understand the factors that contributed to delay and address them. In addition, we will contact all participants on Day 3 after the prescription was sent, and if they have not received the medications, we will encourage them to contact the study site to make other arrangements to obtain the mifepristone and misoprostol.
- If there are 12 cases (3% of total sample) where the participant takes mifepristone after 70 days' gestation, we will assess the need to stop the study. All cases of use past 70 days will be investigated to understand why they occurred and efforts will be made to ensure such errors do not occur in the future. There is evidence that the medication abortion regimen works through 11 weeks of gestation (Kapp, Eckersberger et al. 2019); with regard to clinical safety, this is why the research team feels comfortable with 12 potential cases beyond 70 days gestation. Finally, if 1% of participants (4 cases) take the mifepristone after 84 days (12 weeks), we will stop the study.
- Every AE and SAE will be reviewed by the study PI, and if there is a pattern of definitely-, probably-, or possibly-related SAE/AEs that raise concerns about the safety of the mail-order model of dispensing mifepristone, the study will be stopped. Based on evidence that 0.3% of medication abortions have serious adverse events (Upadhyay, Johns et al. 2018), we will stop the main study if the number of SAEs fall outside of a 95% confidence interval as estimated in a sample of 465 (-0.24% to 0.84%) (minimum sample of 440 plus 25 pilot study participants). Thus we will stop the study if more than 0.84% (n=4) of abortions result in an SAE that is possibly or probably related to the study intervention.

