## 15 DATA SAFETY MONITORING

The site PI will have safety oversight of participants at the site, will assess AEs and SAEs, and will report them to the study PI and research team, who will then report them to the UCSF IRB. Data safety monitoring and review of AEs and SAEs will occur on an ongoing basis through each participant's involvement in the study (up to 6 weeks from day of enrollment). The site PI, in consultation with the study PI, will determine the relationship of the AE to study treatment as definitely related, probably related, possibly related, or unrelated; and the severity of the AE as mild, moderate or severe. For AEs or SAEs that have not resolved at the time of learning of the event, the study team and the site PI will monitor the event until the event is resolved or the study is completed. Because Mifeprex® is already approved, and there is a great deal of safety data on its use for this approved indication, we think it is reasonable for safety monitoring to occur through the standard review of S/AE reports (see section 12).

As part of routine instruction in the FDA's Mifeprex® Medication Guide provided to women undergoing medication abortion, participants will be instructed to return to the study site or a nearby facility offering emergency care in the case of heavy bleeding (more than 2 full-size pads soaked per hour for 2 hours), abdominal pain or "feeling sick", fever of 100.4 degrees or higher persisting more than 4 hours or for any signs of complications.

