### 16.3 Analysis of Primary Endpoint

Acceptability and satisfaction with the mail-order model among patients will be assessed through patient surveys, which will include some open-ended items. The particular variables we will analyze include those on overall satisfaction with the medication abortion service (including whether they would use this mail-order medication abortion service again if they needed another abortion, and whether they would recommend the service to a friend), satisfaction with receiving the medications by mail, reasons for dissatisfaction (open ended questions), and perceptions about the wait time to receive the medications. We will also analyze the reasons why patients who decline participation in the study report not being interested in receiving the medications by mail, as indicated in close-ended and open-ended responses.

We plan to recruit for the main study a minimum sample of 440 participants and a maximum of 625 patients. With the addition of 25 patients in the pilot study, the target minimum number of patients recruited for the study is 465 and the maximum number is 650.

The sample size calculation for this study is based on two measures of acceptability: the proportion of patients who report they would use medication abortion again if they needed another abortion and the proportion who report they were “satisfied” or “very satisfied” with the medication abortion. For both power calculations, we assume 10% loss to follow up, 10% adjustment for clustering, a 5% non-inferiority margin, and a two-sided alpha of 0.05. Research with patients obtaining clinic-based medication abortion has estimated the proportion who would use medication abortion again as 89.7% (Teal, Dempsey-Fanning et al. 2007). Based on our assumptions, with a minimum sample of 440 patients, we will have a final analytic sample of approximately 400 patients, which gives us 79% power to assess this measure of acceptability; with a maximum sample of 625 recruited patients, we will have a final analytic sample of approximately 560 patients, which gives us 92% power.

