## 16.6 Sample Size

In addition to the 25 patients in the pilot study, we aim to recruit a minimum of 440 and a maximum of 625 patients for this study, across 15-20 sites. The sample size calculation for this study is based on a measure of acceptability: the proportion of patients who report they would use medication abortion again if they needed another abortion. Research with patients obtaining clinic-based MA has estimated that proportion as 89.7% (Teal, Dempsey-Fanning et al. 2007). We would like to determine if acceptability of medication abortion when receiving the medications by mail is no more than 5% lower than 89.7%. Assuming 10% loss to follow-up, with a minimum sample of 440 patients, we will have a final analytic sample of approximately 400 patients; with a sample of 625 recruited patients, we will have a final analytic sample of approximately 560 patients. With a 2-sided alpha of 0.05 and 10% adjustment for clustering, a final analytic sample size of approximately 400 gives us 79% power, and an analytic sample of 560 gives us 92% power to assess this measure of acceptability.

We aim to interview all the providers (or staff administrators) involved in medication abortion provision at the study sites, up to 50. This sample size will be determined by the number of providers/staff at the study sites.

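### The numeric SAE stopping rule in section 14.1 gives an interval that does not belong to 465 patients, joins a percentage to a count that disagree within planned enrolment, and leaves out definitely related events

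*Combined protocol and SAP*

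**What the plan says.** The third bullet of section 14.1 contains three sentences that bear on stopping for harm.

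- The first is qualitative. The study PI reviews every event, and the study stops "if there is a pattern of definitely-, probably-, or possibly-related SAE/AEs" raising concern about the safety of mail-order dispensing.
- The second takes a 0.3% SAE rate from a cited study and says "we will stop the main study if the number of SAEs fall outside of a 95% confidence interval". It then gives the source and limits of that interval: "as estimated in a sample of 465 (-0.24% to 0.84%) (minimum sample of 440 plus 25 pilot study participants").
- The third draws the conclusion: "we will stop the study if more than 0.84% (n=4) of abortions result in an SAE that is possibly or probably related", meaning related to the intervention under study.

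Section 15 describes the relatedness scale: the site PI consults the study PI and "will determine the relationship of the AE to study treatment as definitely related, probably related, possibly related, or unrelated". On enrolment, section 16.3 says that "the target minimum number of patients recruited for the study is 465 and the maximum number is 650". Section 16.6 says that "with a minimum sample of 440 patients, we will have a final analytic sample of approximately 400 patients".

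The second bullet of 14.1 has two other limits written as both a count and a percentage. One begins "If there are 12 cases (3% of total sample") and concerns mifepristone taken after 70 days. The other is 4 cases, given as 1% of participants, for use after 84 days.

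**The concern.** This is the only numeric SAE criterion for stopping the study, so its figures have to give one answer. Three things stand in the way.

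1. The interval does not look like the interval for the sample named beside it.
2. The trigger is stated both as a share of abortions and as a count. These can agree only over a limited range of sample sizes, and the plan allows 465 to 650 patients. The wording also leaves open whether the fourth SAE stops the study or whether more than four are needed.
3. The three sentences count different events. The pattern clause includes definitely related events, the interval sentence has no relatedness limit, and the trigger sentence names only possibly and probably related SAEs.

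Two people applying the rule to the same data could reach opposite decisions. If the ambiguity is settled only after events have accrued, the settlement depends on the data.

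**Working it through.** **Inputs.** From 14.1: SAE rate p = 0.003, 95% interval, sample 465, printed limits -0.24% and 0.84%, trigger of more than 0.84% with n = 4. From 16.3: enrolment of 465 to 650 including the 25 pilot patients. From 16.6: analytic sample of about 400 at minimum recruitment.

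**Step 1: the interval.** The printed limits are symmetric about 0.3% (half-width 0.54 points), which points to the normal interval p ± 1.96·√(p(1-p)/n).

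- n = 465: √(0.003 × 0.997/465) = 0.002536; × 1.96 = 0.497 points. Interval **-0.197% to 0.797%**.
- n = 400: half-width 0.536 points. Interval -0.236% to 0.836%, which rounds to the printed pair.
- Over n = 300 to 699, both limits round to -0.24% and 0.84% only for n = 387 to 401.

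Other methods at 465 do not reproduce the printed pair:

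| Variant at 465 | Result |
|---|---|
| multiplier of 2 | -0.21% to 0.81% |
| t quantile | -0.20% to 0.80% |
| continuity correction | upper limit 0.90% |
| Wilson | 0.07% to 1.35% |
| Clopper-Pearson | 0.02% to 1.34% |
| 10% loss | -0.22% to 0.82% |
| clustering factor 1.1 | -0.22% to 0.82% |
| loss and clustering | -0.25% to 0.85% |

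The interval was probably computed for the analytic sample of about 400. That is an inference. It is supported by the two limits in the second bullet of 14.1: 12/0.03 = 400 and 4/0.01 = 400.

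At 465 the correct upper limit is 0.00797 × 465 = 3.71 events and the printed one is 0.0084 × 465 = 3.91 events. The first whole count above either is 4, so this error alone changes no decision at 465.

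**Step 2: the percentage against the count.** For each enrolment N, find the smallest k with k/N > 0.84%. The change points are 4/476 = 0.8403%, 4/477 = 0.8386%, 5/595 = 0.8403% and 5/596 = 0.8389%.

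| Patients | First count above 0.84% | If n = 4 means at least 4 | If n = 4 means more than 4 |
|---|---|---|---|
| 465–476 | 4 | agrees | disagrees |
| 477–595 | 5 | disagrees | agrees |
| 596–650 | 6 | disagrees | disagrees |

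Neither reading agrees with the percentage over the whole planned range, and 14.1 gives no count for samples above 465.

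**Step 3: what the reading changes.** Exact binomial probability of reaching each count at a single look, assuming a true 0.3% rate and every SAE counted as related:

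| Patients | 4 or more | 5 or more | 6 or more |
|---|---|---|---|
| 465 | 5.3% | 1.4% | – |
| 650 | 13.4% | 4.8% | 1.5% |

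If only half of SAEs were judged related (0.15%, an assumption; the documents give no such figure), 4 or more has probability 0.6% at 465 and 1.7% at 650.

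**Step 4: the events counted.** The pattern clause covers definitely, probably and possibly related events. The interval sentence covers all SAEs. The trigger covers possibly or probably related SAEs. Definitely related is a grade of its own in sections 12.1, 12.1.2 (Table 2) and 15, so on its wording the numeric trigger omits it.

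**Minor.** Against planned enrolment, 12 cases are 12/465 = 2.6% to 12/650 = 1.8%, not 3%. Four cases are 4/465 = 0.86% to 4/650 = 0.62%, not 1%. Those counts can still be applied as written.

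**The case against.** The strongest reply is that the rule names its own base. The sentence refers to 465 patients; there 0.84% is 3.9 events and 4/465 = 0.86% exceeds it, so the count of 4 is simply the stopping count at that sample. On this view the conflict arises only when the percentage is carried to sample sizes the sentence does not mention, and the interval slip has no effect. The missing word is a drafting omission: the trigger sentence follows from one that counts all SAEs, the pattern clause includes definitely related events, and the study PI reviews every SAE and can stop at any count.

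Much of this is right. At 465, and up to 476, stopping at four agrees with the percentage. Definitely related events are not outside all stopping review. But the plan allows 650 patients, the trigger is written as a share of abortions, and no count is given beyond 465. Placing the count after the words for exceeding a percentage leaves the fourth-or-fifth question open even at 465. A judgement-based backstop does not make the numeric rule readable.

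A second objection is that review is ongoing, so the 1.5% for six or more at 650 understates how often a running 0.84% limit would be crossed. That is correct: 1.5% is a single-look figure. If the percentage were checked after each patient at a true 0.3% rate, it would be crossed with probability 6.5% somewhere between 465 and 650, and 35% counting from the first patient, since one SAE among the first 119 patients already exceeds 0.84% (1/119 = 0.8403%). This is a further reason to state the denominator.

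**Conclusion.** The concern holds and must be fixed. The printed interval is wrong for 465 patients (-0.20% to 0.80% is correct under the normal formula), though this does not alter the count at 465. The percentage and the count are not one rule over 465 to 650 patients: they disagree at 477–650 on one reading, and at 465–476 and 596–650 on the other. At 650 the rule can be read as stopping at 4, 5 or 6 SAEs, with single-look chance probabilities from 13.4% down to 1.5%. Those probabilities assume a true 0.3% rate with every SAE counted as related; the disagreement itself rests only on the documents' own figures. The numeric trigger also omits definitely related SAEs by its wording, although the pattern clause still covers them.

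**What to change.** Revise the wording of section 14.1:

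- Correct the interval to the sample stated, or state the sample actually used.
- Reconcile the percentage and the count into one trigger. State its denominator (including whether the 25 pilot patients count and what applies while enrolment is still below 465), whether it means at least or more than, and the count that applies at each enrolment up to 650.
- Use one relatedness definition across the three sentences, so that definitely related SAEs are not left out of the numeric rule by omission.
- As a minor point, state the denominator behind the 3% and 1% in the second bullet.

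The sponsor keeps the choice of threshold; the requirement is that the figures agree with each other. The cost is a protocol wording change, with no new data and no additional patients.

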## 15 DATA SAFETY MONITORING

The site PI will have safety oversight of participants at the site, will assess AEs and SAEs, and will report them to the study PI and research team, who will then report them to the UCSF IRB. Data safety monitoring and review of AEs and SAEs will occur on an ongoing basis through each participant's involvement in the study (up to 6 weeks from day of enrollment). The site PI, in consultation with the study PI, will determine the relationship of the AE to study treatment as definitely related, probably related, possibly related, or unrelated; and the severity of the AE as mild, moderate or severe. For AEs or SAEs that have not resolved at the time of learning of the event, the study team and the site PI will monitor the event until the event is resolved or the study is completed. Because Mifeprex® is already approved, and there is a great deal of safety data on its use for this approved indication, we think it is reasonable for safety monitoring to occur through the standard review of S/AE reports (see section 12).

As part of routine instruction in the FDA's Mifeprex® Medication Guide provided to women undergoing medication abortion, participants will be instructed to return to the study site or a nearby facility offering emergency care in the case of heavy bleeding (more than 2 full-size pads soaked per hour for 2 hours), abdominal pain or "feeling sick", fever of 100.4 degrees or higher persisting more than 4 hours or for any signs of complications.

## 16 STATISTICAL METHODS AND CONSIDERATIONS

Prior to the analysis of the final study data, a detailed Statistical Analysis Plan (SAP) will be written describing all analyses that will be performed. The SAP will contain any modifications to the analysis plan described below.

### 16.1 Data Sets Analyzed

All eligible patients who receive the dose of the study drug will be included in the analysis. All eligible providers who complete an interview will be included in the provider analysis.

### 16.2 Demographic and Baseline Characteristics

The demographic information that will be collected: Age, parity, race/ethnicity. At the initial visit, we will also collect: date of service, gestational age and method of determining gestational age, past medical and surgical history, current medications, and medications prescribed or dispensed. Blood pressure, weight, and height will be collected. All participants will receive the same dose of Mifeprex®.

### 16.3 Analysis of Primary Endpoint

Acceptability and satisfaction with the mail-order model among patients will be assessed through patient surveys, which will include some open-ended items. The particular variables we will analyze include those on overall satisfaction with the medication abortion service (including whether they would use this mail-order medication abortion service again if they needed another abortion, and whether they would recommend the service to a friend), satisfaction with receiving the medications by mail, reasons for dissatisfaction (open ended questions), and perceptions about the wait time to receive the medications. We will also analyze the reasons why patients who decline participation in the study report not being interested in receiving the medications by mail, as indicated in close-ended and open-ended responses.

We plan to recruit for the main study a minimum sample of 440 participants and a maximum of 625 patients. With the addition of 25 patients in the pilot study, the target minimum number of patients recruited for the study is 465 and the maximum number is 650.

The sample size calculation for this study is based on two measures of acceptability: the proportion of patients who report they would use medication abortion again if they needed another abortion and the proportion who report they were “satisfied” or “very satisfied” with the medication abortion. For both power calculations, we assume 10% loss to follow up, 10% adjustment for clustering, a 5% non-inferiority margin, and a two-sided alpha of 0.05. Research with patients obtaining clinic-based medication abortion has estimated the proportion who would use medication abortion again as 89.7% (Teal, Dempsey-Fanning et al. 2007). Based on our assumptions, with a minimum sample of 440 patients, we will have a final analytic sample of approximately 400 patients, which gives us 79% power to assess this measure of acceptability; with a maximum sample of 625 recruited patients, we will have a final analytic sample of approximately 560 patients, which gives us 92% power.

A meta-analysis reviewed 8 studies investigating satisfaction with medication abortion (Ngo 2011); of those who had a home-based medication abortion (n=3,138), the average proportion reporting they were “satisfied or highly satisfied” was 88.4%. Based on our assumptions, with a minimum sample of 440 patients, we will have a final analytic sample of approximately 400 patients, which gives us 77% power to assess this measure of acceptability; with a sample of 625 recruited patients, we will have a final analytic sample of approximately 560 patients, which gives us 90% power.

## 16.4 Analysis of Secondary Endpoints

Feasibility of the mail-order pharmacy dispensing model will be assessed through surveys with patients, and include determination of the proportion of patients who receive the medications by Day 2 and by Day 3 after the prescription is sent, the quality of the packaging, whether patient confidentiality was compromised due to receiving the medications by mail, as well as the proportion of patients who had to go to the clinic to obtain the medications.

Clinical effectiveness and safety outcomes, including adverse events, with medication abortion obtained via mail-order pharmacy will be assessed using quantitative data abstracted from patient medical records, as well as information on clinical outcomes captured in the Day 14 patient survey. The analysis populations for the effectiveness and safety endpoints will include patients who enroll in the study, take either of the medications, and for whom we have follow-up data. We will not assume that patients who do not have follow-up data had a successful abortion.

Effectiveness will be defined as the successful completion of abortion (versus incomplete abortion or continuing pregnancy), without vacuum aspiration. Continuing pregnancy will be defined as a viable pregnancy following treatment and need for vacuum aspiration to terminate the pregnancy or cases where a patient elects to continue the pregnancy after failed treatment (Creinin & Chen 2016). We will document vacuum aspiration abortions, including reasons for aspiration, reported by participants and those determined as necessary by the study providers at follow-up visits. We will compare effectiveness (the proportion of our sample that experiences a complete abortion not requiring vacuum aspiration) with published estimates (97.4%) (FDA 2016), using an exact binomial test. Assuming 10% loss to follow-up and 10% adjustment for clustering, and a two-sided alpha of 0.025 (to account for type I error), we estimate that a final analytic sample ranging from approximately 400 to 560 patients gives us 98% to 100% power to determine that mail-order medication abortion is as effective as in-person dispensing, if effectiveness in the mail-order model is no lower than 92.4%. A non-inferiority limit is defined as -5% and as an acceptable difference in the proportion of complete abortions.

We are unable to similarly assess whether the prevalence of clinically significant adverse events differs between the mail-order dispensing model and historical controls given the very low frequency of this outcome (<0.5%) (Upadhyay, Desai et al. 2015). A sample size of over 10,000 is required to power such an analysis and is not feasible in the proposed study. Thus, our analysis of safety outcomes will be exploratory. Using a patient survey and medical record review, we will thoroughly document women's experiences with any adverse events. In particular we will be interested in documenting adverse events that could be related to mail-order dispensing. For example, if the delivery of the medication was delayed, which caused a patient to undergo medication abortion after 70 days gestation and she had heavy bleeding requiring an emergency department visit, we would consider this to be possibly related to the mail-order dispensing model. Additional safety outcomes include the proportion of participants who take mifepristone after 70 days gestation and the proportion that divert the medication to someone else.

Provider acceptability, including clinician and staff perspectives on the timing and logistics, quality of care, clinic flow, cost, and sustainability of the mail-order dispensing of mifepristone and misoprostol, will be explored through qualitative analysis of in-depth open-ended interviews. We will invite all clinicians and staff who were involved in identifying and recruiting patients, communicating with the mail-order pharmacy, and/or following up with patients about their clinical care in the study, to participate in an interview at the end of the study period.

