### 2.1 Risk / Benefit Assessment

Potential medical risks to medication abortion patients participating in the study are the same as those they would incur by undergoing a medication abortion outside of the study. Because they are undergoing the same clinical assessment prior to obtaining MA, there is no reason to believe that dispensing of Mifeprex® by pharmacists will increase the risks of the procedure. In addition, patients will be given detailed information about warning signs, such as heavy bleeding, that should prompt them to seek care.

The main risk related to the study is that the patient may not take Mifepristone® at the time they are told to—and potentially that they may take it later than 70 days' gestation (the current FDA gestational age limit). There is also a risk that they may give the medication to someone else. It should be noted that these risks exist currently since the Mifepristone® label allows them to take the medication at home, and there is no reason to believe that the risks will increase due to the study. Patients will also be surveyed on Day 3 to be certain they received and took the Mifepristone® as instructed. The eligibility criteria for this study will limit gestational age of participants to 63 days at the time of prescribing, so as to minimize the risk of patients taking the medications after 70 days due to delays in receiving the drugs. Women who do not return for follow-up at the clinic will be contacted by phone or email to obtain information about abortion completion and adverse events. Other potential risks include any social risks involved if information they reveal about their seeking an abortion or other sensitive issues were to be disclosed outside of the research.

There are minimal risks to providers for participating in the study. The participating clinics will not be identified in any publications. There is a potential risk that participating clinics will experience anti-abortion picketers if participation in the study becomes known, and this has been discussed with the management of each clinic.

These data will be used to assess whether it is feasible for ob/gyn and primary care clinics to provide medication abortion and for patients to receive the medications by mail, which could help to improve access to early abortion.

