## 12 ADVERSE EXPERIENCE REPORTING AND DOCUMENTATION

### 12.1 Adverse Events

Adverse Events (AEs) are to be reported only for untoward medical events that occur in participants after they have enrolled in the study. Only new untoward events, or a worsening of an existing condition, are considered AEs. Conditions that were present before enrollment into the study, and that remain stable or improve during the study, are not considered AEs. Only serious or unexpected AEs that are possibly, probably, or definitely related to the research will be submitted to the UCSF IRB. Diversion of Mifeprex® obtained in the study to someone other than the participant will also be considered an AE.

Information regarding AEs or SAEs may be first obtained by the clinical or study staff, as both will communicate with the participant at her visits and by phone.

Details about each AE or SAE will be recorded on an AE/SAE Form. This form will require the following information to be collected: diagnosis, onset date, resolution date, source of information, severity, treatment given, relationship to the study, action taken, and comments.

The physician site PI will have safety oversight of participants at the site, will assess AEs and SAEs, and will report them to the study PI and research team, who will then report to the UCSF IRB as

needed. The site PI, in consultation with the study PI, will determine the relationship of the AE to study treatment as definitely related, probably related, possibly related, or unrelated; and the severity of the AE as mild, moderate or severe. For AEs or SAEs that have not resolved at the time of learning of the event, the study team and the site PI will monitor the event until the event is resolved or has stabilized.

The study PI is also responsible for reporting all AEs to all relevant Institutional Review Boards (IRBs). All AEs that are related to the study and are serious or affect IRB approval will be reported by the PI to the relevant IRBs according to IRB requirements. UCSF requires that an internal (on-site) AE that the PI determines to be related to the study and serious or unexpected shall be reported within 5 working days of the UCSF PI's knowledge. External (off-site) AE's that change the study risks/benefits or requires a UCSF IRB modification must be reported within 10 working days of the UCSF PI's knowledge. Diversion of Mifeprex® will be reported to the FDA within 15 days of the UCSF PI's knowledge.

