### **12.2.1 Serious Adverse Event Reporting**

Study sites will document all SAEs that occur (whether or not related to study drug) per [UCSF IRB Guidelines](#). The collection period for all SAEs will begin after informed consent is obtained and end six weeks after the visit where Mifeprex® is prescribed.

In accordance with the standard operating procedures and policies of the local IRB/the site PI will report SAEs to the IRB.

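### Section 16.4 counts diversion only among participants who took a study medication, so those who gave away the whole package drop out and the reported proportion is biased toward zero

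*Combined protocol and SAP*

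**What the plan says.** Section 16.4 (Analysis of Secondary Endpoints) defines a single population for effectiveness and safety. The effectiveness and "safety endpoints will include patients who enroll in the study, take either of the medications, and for whom we have follow-up data". Three conditions apply: enrolment, intake of at least one of the two drugs, and follow-up data.

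Later in 16.4 the additional safety outcomes are named as "the proportion of participants who take mifepristone after 70 days gestation and the proportion that divert the medication to someone else". No separate denominator is given for either. The section also states that "our analysis of safety outcomes will be exploratory".

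Elsewhere the protocol treats diversion as a risk to be tracked. Section 2.1 says "There is also a risk that they may give the medication to someone else". Section 12.1 says "Diversion of Mifeprex® obtained in the study to someone other than the participant will also be considered an AE", and requires such cases to be reported to the FDA within 15 days of the study PI learning of them. The Day 3 survey (10.2) asks about diversion of both drugs.

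Event collection starts before intake. Section 12.1 covers untoward events after enrolment, and 12.2.1 says "The collection period for all SAEs will begin after informed consent is obtained".

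Section 16.1 uses a different condition: "All eligible patients who receive the dose of the study drug will be included in the analysis". It does not say whether receiving means that the drug was delivered or that it was taken.

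**The concern.** Intake is the right condition for effectiveness, for events after intake, and for mifepristone taken past 70 days. It is the wrong condition for diversion, because giving the drugs away is a reason for not having taken them. The most complete form of the outcome removes the participant from the set in which the outcome is counted.

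Diversion is one of the drug-handling risks that 2.1 names, and the study is meant to inform possible changes to the dispensing restriction (section 2). A published diversion proportion lower than the AE log and the FDA reports imply would mislead, even with an exploratory label.

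The same condition affects adverse events. Section 6.1 foresees participants whose package does not arrive within 3 days and who are referred elsewhere. If such a participant never takes a drug, an event she has is collected but lies outside the 16.4 safety set. Section 16.4 also expresses particular interest in events that could be related to mail-order dispensing.

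**Working it through.** **The plan's own figure.** The documents give no diversion rate, threshold or denominator, so there is nothing to reproduce for the outcome itself. The analytic sample sizes used as scenario denominators do reproduce: 440 × 0.9 = 396 (stated as about 400) and 625 × 0.9 = 562.5 (stated as about 560).

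**Who is in the 16.4 set.** Mifeprex is supplied as one 200 mg tablet (8.3.2), so a participant who gives it away has not taken that tablet.

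- Gave away both drugs and took neither: out of numerator and denominator.
- Gave away Mifeprex and took misoprostol: in, if followed up.
- Took Mifeprex and gave away misoprostol: in, if followed up.

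Section 8.6 foresees both one-drug intake patterns.

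**Formula.** Let N be recipients with follow-up, D the diverters among them, and f the share of diverters who took neither drug.

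- Proportion among recipients: D / N
- Proportion in the 16.4 set: D(1 − f) / (N − Df)

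D and f are assumptions, since the documents give neither.

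**Numbers put in**, for N = 400, D = 12, f = 0.5: 12 × 0.5 / (400 − 6) = 6/394 = 1.52%, against 12/400 = 3.00%.

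| N | D | Among recipients | f = 1 | f = 0.75 | f = 0.5 | f = 0.25 | f = 0 |
|---|---|---|---|---|---|---|---|
| 400 | 4 | 1.00% | 0.00% | 0.25% | 0.50% | 0.75% | 1.00% |
| 400 | 12 | 3.00% | 0.00% | 0.77% | 1.52% | 2.27% | 3.00% |
| 400 | 20 | 5.00% | 0.00% | 1.30% | 2.56% | 3.80% | 5.00% |
| 560 | 12 | 2.14% | 0.00% | 0.54% | 1.08% | 1.62% | 2.14% |

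The written set understates the proportion whenever f is above 0, and returns zero only when f = 1. When f = 0 there is no bias.

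**Adverse events.** Set side by side, 12.1 and 12.2.1 collect events from enrolment or consent, while 16.4 analyses only those who took a drug. The difference is events in enrolled participants who never took one. The documents give no basis for a count, so this part has no figure.

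**Two features that add to the gap.** Section 16.4 names medical records and the Day 14 survey as sources for safety outcomes, and later only an unspecified patient survey; the diversion question is in the Day 3 survey. Section 13.3 replaces subjects who withdraw before taking the drugs, so a whole-package diverter who withdraws is replaced in the target sample. The final report is to mention replacement, but nothing puts these subjects in the diversion denominator.

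**The case against.** **The result would not be near zero whatever happened.** A reader might infer that it would. The documents do not support that: the set requires intake of only one of the two drugs, so one-drug diverters stay in. The bias depends on a split that the documents do not give.

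**Whole-package diversion is not always excluded.** Under 6.1 a participant whose package is late may obtain medication elsewhere or return to the study site. If she then receives the mailed package and gives it away, she has taken medication, and 16.4 does not say from which source it must come. This stands, but covers only participants who were re-supplied.

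**Harms during the mail wait are not removed as a class.** A reader might infer that they are. Section 16.4 selects participants, not time windows. Someone who has an event while waiting, then takes the drug and is followed up, is analysed. Only events in never-takers fall outside, and those are still collected and reviewed under 12.1, 12.2.1 and 14.1.

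**Diversion would not go unseen.** The Day 3 survey asks about it, Mifeprex diversion is an AE, and each case goes to the FDA, all independently of any analysis set. Diversion carries no hypothesis, power figure or stopping criterion. Section 2.1 adds that the risk already exists with home use and is not expected to rise. This stands, and it lowers the severity. It does not correct the proportion that 16.4 would report.

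**Section 16.1, or the later SAP, could settle it.** Section 16.1 refers to receiving the dose, but 16.4 is the specific rule for safety endpoints and 16.1 does not override it. Section 16 promises a detailed SAP that may modify the plan. That is a good place for the correction, but the current text gives a denominator that is wrong for this outcome.

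**Conclusion.** The point holds as a bias in one reported safety outcome. Followed as written, 16.4 leaves out anyone who gave away the whole package and took neither drug, so "the proportion that divert the medication to someone else" is pulled toward zero, and to exactly zero if all diverters are of that kind. With an assumed 12 diverters among 400 recipients, a 3.0% proportion would be reported as anything from 0% to 3.0%. Both the number of diverters and the split are assumptions. The calculation also takes all recipients as followed up and no diverter as re-supplied.

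The second part is narrower: the set omits AEs and SAEs only in enrolled participants who never took a drug.

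Severity is moderate. The outcome is exploratory, the cases are captured elsewhere, and no power figure, sample size or stopping rule changes.

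**What to change.** In 16.4:

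1. Keep the takers-with-follow-up set for effectiveness and for adverse events after intake.
2. Report diversion of either drug over all participants to whom a package was dispensed, including those replaced under 13.3. Take cases from the Day 3 survey, the AE forms and the drug accountability log (8.5). Show unaccounted-for packages separately, so that missing information is not read as no diversion.
3. Report SAEs, and the clinically significant adverse events defined in 4.3, also over all enrolled participants from consent, to match the collection rule in 12.2.1.
4. State what receiving the dose means in 16.1 and reconcile it with the intake condition in 16.4.

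The cost is wording in the protocol and the SAP plus one or two table rows. The data are already to be collected. The diversion rate may look slightly less favourable than under the present set.
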